8.8.1.6. Follow-up for AEs and SAEs

The investigator is obligated to perform or arrange for the conduct of supplemental measurements and/or evaluations as medically indicated to elucidate the nature and/or causality

of the AE or SAE as fully as possible. This may include additional laboratory tests or investigations or consultation with other health care professionals.

Urgent safety queries must be followed up and addressed promptly. The investigator will submit any updated SAE data to the CRO within 24 hours of receipt of the information. Follow-up information and response to non-urgent safety queries should be combined for reporting to provide the most complete data possible within each follow-up report.

8.8.1.7. Adverse Events of Special Interest

AESIs comprise respiratory tract infections, including COVID-19, and herpes zoster. All AESIs (serious and non-serious) should be reported within 24 hours of the investigator's awareness of the event with an assessment of seriousness, causality, and a detailed narrative. Serious AESIs should be reported by the investigator using the paper SAVER form and non-serious AESIs should be reported by completing the adverse event CRF page.

Combined elevations of aminotransferases and bilirubin, either serious or nonserious and whether or not causally related, meeting the laboratory criteria of a potential Hy's Law case (ALT or AST $\geq 3 \times$ ULN with simultaneous total bilirubin $\geq 2 \times$ ULN) should always be reported to the Sponsor using a special collection eCRF, with the investigator's assessment of seriousness, causality, and a detailed narrative. These events must be reported within 24 hours of investigator's awareness of the event.

If the subject discontinues study drug due to liver enzyme abnormalities, the subject should have additional clinical and laboratory evaluations in order to determine the nature and severity of the potential liver injury.

8.8.1.8. Overdose

An overdose is defined as the accidental or intentional administration of any dose of a product that is considered both excessive and medically important. All occurrences of overdose must be reported to the Sponsor within 24 hours of awareness.

Overdose will be reported via eCRF. An "excessive and medically important" overdose includes any overdose in which either an SAE or a non-serious AE (Section 8.8.1), or no AE occurs and is considered by the investigator as clinically significant, ie, poses an actual or potential risk to the subject.

Occupational exposures must be reported via EDC.

Overdoses are not expected in this study in which the study drug is monitored at all times by the clinical site staff. The pharmacist and the pharmacy staff are responsible for correctly preparing the study drug for delivery by the staff to the subjects.

8.8.1.9. Pregnancy

It is the responsibility of the investigator or designee to notify the Sponsor of any pregnancy in a female subject or a male subject's female partner that occurs after the subject receives DS-7011a through the EOS Visit. Although pregnancy is not technically an AE, all pregnancies must be followed to conclusion to determine their outcome. If a pregnancy is reported, the investigator, or designee, must report any pregnancy in a female subject using the Exposure In Utero (EIU)

Reporting form within 24 hours of learning of the pregnancy, as this information is important for drug safety and public health concerns.

The investigator should make every effort to follow the partner of a male subject (upon obtaining written consent from her) until completion of the pregnancy and to document the complete pregnancy outcome information, including normal delivery or induced abortion. Any adverse pregnancy outcome, either serious or non-serious, should be reported in accordance with study procedures. If the outcome of the pregnancy meets the criteria for immediate classification as an SAE (ie, post-partum complications, spontaneous or induced abortion, stillbirth, neonatal death, or congenital anomaly, including that in an aborted fetus), the investigator should follow the procedures for reporting SAEs.

For reports of pregnancy in a female partner of a male subject, the EIU Reporting Form (or SAE form if associated with an adverse outcome) should be completed with the details regarding the female partner entered in the narrative section.

8.8.1.10. Pregnancy Testing

Women of childbearing potential who follow the contraception requirements of the study will be included in the study. A serum pregnancy test will be conducted on all females of childbearing potential at Screening so that results are available before enrollment. A urine pregnancy test will be conducted on all females of childbearing potential on Day 1, Day 29, Day 57, Day 85, and Day 113 (Final Visit) to rule out any change in status.

Women claiming postmenopausal status may have an FSH test conducted at Screening according to investigator's decision.

8.8.2. Reporting of Exposure to COVID-19 (SARS-CoV-2)

All confirmed or suspected COVID-19 events must be recorded in the eCRF.

- Subjects who test positive for COVID-19 should be reported as "Confirmed COVID-19," either as an AE or SAE.

The usual protocol mandated SAE reporting requirements should be followed for confirmed or suspected COVID-19 (or SARS-CoV-2) as done for any other AE, ie, the investigator should assess whether any seriousness criteria are met per protocol, and appropriate protocol reporting requirements should be followed.

In the event that the investigator assesses that a COVID-19 case does not meet any seriousness criteria as outlined in the protocol, it should be reported as a non-serious AE in the eCRF.

All study drug interruption or discontinuation due to the COVID-19 event must be recorded on the AE and drug administration eCRFs.

For both serious and non-serious COVID-related AEs, the following information should be provided as applicable:

- Date and laboratory results confirming the COVID-19 diagnosis (including viral antigen test and/or antiviral antibody serological test) in the eCRF.

- Clinical course of the case, including presenting signs, symptoms, exposure, actions taken with the study drug, medications used for treatment or prophylaxis of COVID-19, and outcome in relevant eCRF (eg, concomitant medication, AE).
- Findings from diagnostic imaging (including computed tomography scan or other chest imaging).

8.8.3. Clinical Laboratory Evaluations

Blood and urine will be collected for clinical chemistry, hematology, and coagulation tests and for urinalysis at Screening, Day 1, and at subsequent visits as detailed in the SoE ([Table 1.1](#)). Blood for virology will be collected at Screening. Urine tests for drugs of abuse, cotinine, and alcohol will be conducted at Screening.

A nasal (or pharyngeal or oral) swab for COVID-19 testing will be obtained at Screening and on Days 1, 29, and 57.

Refer to Section [10.3](#) for the complete list of laboratory parameters.

Abnormal laboratory values occurring during the clinical study will be followed until repeat test results return to normal (or baseline), stabilize, or are no longer clinically significant. New or worsened clinically significant laboratory abnormalities should be recorded as AEs.

8.8.4. Physical Examinations

Physical examinations will be performed at Screening, Day 1, Day 29, Day 57, Day 85, and Day 113 as shown in the SoE ([Table 1.1](#)).

A full physical examination should include an evaluation of the head, eyes, ears, nose, and throat and the cardiovascular, dermatological, musculoskeletal, respiratory, gastrointestinal, and neurological systems.

Any abnormality in physical examination should be recorded. New or worsened clinically significant abnormalities should be recorded as AEs.

8.8.5. Vital Signs

Vital signs will be collected at Screening, Day 1, and before each PK/PD blood draw during the study as detailed in the SoE in [Table 1.1](#).

Allowable time windows for vital sign assessments are provided in Section [10.5](#).

Vital signs will include the measurements of respiratory rate, heart rate, systolic and diastolic blood pressures, and temperature. Vital signs will be measured after the subject has rested in a supine position for at least 5 minutes, prior to laboratory draws and prior to ECG measurements when they are scheduled at the same time points.

8.8.6. Electrocardiograms

Triplicate ECGs (approximately 1 minute apart) will be taken at Screening, on Day 85 and on Day 113 as shown in the SoE ([Table 1.1](#)). ECGs will be obtained after the subject has rested in a supine position for at least 5 minutes. When a blood collection is scheduled concomitantly with an ECG, the ECG should be taken at least 5 minutes prior to the blood collection.

Allowable time windows for ECGs are provided in Section [10.5](#).

At any visit during which a subject exhibits ECG abnormalities (eg, a heart rate ≤ 50 bpm) based on triplicate ECG readings, additional readings may be performed according to the investigator's discretion. ECG abnormalities that are considered clinically significant and that occur after the study drug administration will be reported as AEs. The following information will be recorded for any visit foreseeing ECG reading: Confirmation if ECG reading was indeed performed or not, date, and values of heart rate, PR interval, RR interval, QT interval, and QTcF interval.

8.8.7. Immunoglobulin (IgM, IgG, and IgA) Values

Blood will be collected for the determination of the circulating values of total IgM, IgG, and IgA, at predose on Day 1 on Day 85, and on Day 113.

8.8.8. Vaccine (Diphtheria, Tetanus, and Pneumococcus) Titers

Blood will be collected on Day 1, on Day 85, and on Day 113 for the determination of the circulating titers of Ab raised by possible prior vaccinations against diphtheria, tetanus, and pneumococcus.

8.8.9. Lymphocyte Subset (CD3-, CD4-, CD8-, CD20-, CD16-, CD56-Positive) Values

Blood will be collected for the determination of the following circulating lymphocyte subsets: CD3-, CD4-, CD8-, CD20-, CD16-, CD56-positive. This collection will be at Screening, at predose on Day 1, and at subsequent visits as detailed in the SoE ([Table 1.1](#)) until Day 113.

9. STATISTICAL CONSIDERATIONS

9.1. Statistical Hypothesis

This is not a hypothesis testing study.

9.2. Sample Size Determination

The study will enroll up to 24 subjects with SLE in 2 parallel arms randomized to receive 2:1 DS-7011a or placebo. Tentatively, 9 of these 24 subjects will be of African descent. Also, tentatively, 9 of these 24 subjects will be positive for anti-Sm and/or anti-RNP autoantibodies.

The sample size selected is not based on statistical power considerations. The number of subjects in each arm is considered sufficient to achieve the objectives of this study. Initial evidence of DS-7011a efficacy will be inferred by the impact DS-7011a shows on clinical endpoints, mainly CLASI-A, and several mechanistic endpoints. This impact will be evinced by comparing endpoint values between DS-7011a-treated and placebo-treated subjects and between pretreatment (baseline) and post-treatment time points. Concomitant and consistent impact on multiple endpoints will be initial evidence of efficacy, especially if this impact is of large extent. DS-7011a extent of impact will be compared to that reported for antibodies approved (belimumab and anifrolumab) or in late phase of development (BIIB059) for the treatment of SLE². The result of this comparison will inform a DS-7011a “go/no-go” decision to further development.

9.3. Exposure and Compliance

As study drug administration is under the control of the personnel at the clinical study site, compliance to study medication will not be an issue.

9.4. Population for Analysis Sets

9.4.1. Pharmacokinetic Analysis Set

The PK analysis will be conducted on the PK Population defined as all subjects who received at least one infusion of study drug and have at least one measurable PK result. PK parameters will include but not be limited to: C_{max} , C_{min} , AUC_t , $t_{1/2}$, CL, and V_{ss} .

9.4.2. Safety Analysis Set

The safety analysis will be conducted on the Safety Analysis Set defined as all subjects who received at least 1 infusion of study drug.

9.4.3. Intent-to-treat Analysis Set

The Intent-to-Treat (ITT) Analysis Set will consist of all subjects who are randomized.

9.4.4. Modified Intent-to-treat Analysis Set

The Modified Intent-to-Treat (mITT) Analysis Set will consist of all randomized subjects who received at least one infusion of study drug.

9.5. Statistical Analysis

The statistical analysis plan (SAP) will be developed and finalized before database lock and will describe the subject populations to be included in the analyses, and procedures for accounting for missing, unused, and spurious data.

The following sections of the protocol summarize the planned statistical analyses of the primary, secondary, and exploratory endpoints.

9.5.1. Efficacy Analysis

No primary efficacy measures or analysis are planned for this study; all efficacy measures will be secondary analyses.

All secondary efficacy analyses will be based on the mITT Analysis Set. The efficacy endpoints (CLASI-A, CLA-IGA, SLEDAI-2K, PGA-SLE, CGI-C, and PROs) will be summarized by treatment group using descriptive statistics. Comparison between treatment groups for the change from baseline to each visit in CLASI-A, CLA-IGA, SLEDAI-2K, PGA-SLE, CGI-C, and PROs, and laboratory parameters, such as autoantibodies (including antinuclear, anti-dsDNA, anti-Sm, and anti-RNP antibodies), complement factors (C3, C4), ESR, and CRP, will be summarized.

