3.1. Rationale for Selection of Primary Endpoints and Key Secondary and Exploratory Endpoints

The main scope of this Phase 1b/2 study is to explore DS-7011a safety and tolerability as primary objectives, to explore efficacy, PK, and immunogenicity properties as secondary objectives, and to explore PD properties as exploratory objectives. The rationale for the selection of IgM, IgG, and IgA values, vaccine (diphtheria, tetanus, and pneumococcus) titers, and lymphocyte subset (CD3-, CD4-, CD8-, CD20-, CD16-, and CD56-positive) values should allow an initial insight into DS-7011a immunosuppressive potential. Regarding clinical efficacy endpoints, in addition to overall SLE parameters, the selection of parameters such as the Cutaneous Lupus Area and Severity Index Activity (CLASI-A), which are descriptive of CLE, should favor an initial detection of potential for beneficial clinical activity, given the expectation that TLR7 plays a particularly prominent role in the development of this component of the SLE disease. Regarding clinical laboratory efficacy and PD endpoints, the selection of biomarkers reflects their mechanistic proximity to TLR7 activation (TLR7 GS expression), TLR7 role in SLE pathogenesis (cytokines and autoantibody concentrations), and inflammatory effects that cytokines and autoantibodies have (complement factors and MxA and inflammatory cell marker mRNA). Anti-Sm and anti-RNP autoantibodies will be assessed with particular interest, since their production may especially depend on TLR7 and therefore be blocked by DS-7011a.

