5.1. Inclusion Criteria

Subjects eligible for inclusion in this study have to meet all inclusion criteria for this study:

1. Male and female subjects must be of 18 years or more with definite SLE for at least 6 months prior to Screening, defined according to the 2019 European League Against Rheumatism (EULAR)/ American College of Rheumatology (ACR) classification criteria for SLE³, including documented history of positivity for antinuclear antibody (titer $\geq 1:80$).
2. Body mass index (BMI) ≥ 18 kg/m².
3. Presence of active CLE (acute, subacute, and chronic cutaneous lupus) with active skin involvement and a CLASI-A score of 4 or higher at the time of Screening and randomization, as recognized by 2 adjudicators, ie, the investigator in the periphery at the site and a centrally located arbiter contracted ad hoc (in case of disagreement between these 2 adjudicators, a third adjudicator, also centrally located and contracted ad hoc, will solve the disagreement and provide a final decision), despite adequate use of conventional therapies (either topical corticosteroids or antimalarial agents used for at least 12 weeks prior to Screening) or because of the requirement to discontinue these therapies due to side effects or poor tolerability.
4. Subjects must be willing to have skin tape harvests collected from the affected skin area (skin tape stripping done on the target lesion).
5. If the subject is a female of childbearing potential, she must have a negative serum pregnancy test at Screening and a negative urine pregnancy test at randomization, and she must be willing to use one method of highly effective birth control, as detailed in Section 10.2, and one barrier method, such as condom, diaphragm, or cervical cap with spermicide, upon enrollment, during the Treatment Period, and for 3 months following the last dose of study drug. A female is considered of childbearing potential following menarche and until reaching postmenopausal state, which is defined as no menstrual periods for a minimum of 12 months (a follicle-stimulating hormone [FSH] test may be conducted to confirm postmenopausal state according to investigator's discretion), unless made permanently sterile by surgery (undergone a hysterectomy, bilateral salpingectomy, or bilateral oophorectomy at least 1 month before the first dose).

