8.5. Randomization

Subjects who meet the eligibility criteria and provide signed informed consent will be randomly assigned on Day 1 to 1 of 2 treatment arms to receive 2:1 DS-7011a or placebo. Study drug will be administered following randomization assignment based on the subject's weight (mg/kg basis) on Day 1.

Subjects who withdraw from the study may be replaced after consultation with the Sponsor. The study will allow up to 3 replacements for a subject with an assigned treatment.

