9.5.5. Pharmacodynamic Analysis

Pharmacodynamic measures will be evaluated as exploratory analyses.

The pharmacodynamic endpoints (mechanistic endpoints) will be summarized by treatment group using descriptive statistics. Comparison between treatment groups for the change from baseline to each visit in several endpoints indicative of mechanistic efficacy, including, but not limited to: circulating TLR7 and IFN-Type I GS; skin mRNA coding for proteins under IFN-Type I regulation, such as MxA, and for markers of inflammatory cells, such as CD45; and cytokines, will be summarized.

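### No baseline adjustment is prespecified for the between-arm CLASI-A comparison, and uncontrolled pre/post change counts towards the go/no-go decision without ranking below the randomised contrast

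*Combined protocol and SAP*

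**What the plan says.** Section 9.5.1 summarises the efficacy endpoints descriptively by arm and adds a "Comparison between treatment groups for the change from baseline to each visit in CLASI-A, CLA-IGA, SLEDAI-2K, PGA-SLE, CGI-C, and PROs", with the laboratory parameters treated the same way. Section 9.5.5 uses the same form for the pharmacodynamic endpoints: "Comparison between treatment groups for the change from baseline to each visit in several endpoints indicative of mechanistic efficacy". Neither section names a model, a baseline covariate, an interval or a decision visit.

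Section 9.2 says the drug's impact, mainly on CLASI-A, will be shown by "comparing endpoint values between DS-7011a-treated and placebo-treated subjects and between pretreatment (baseline) and post-treatment time points". The size of that impact is then set against other antibodies and informs the go/no-go decision. Section 9.2 does not rank the two kinds of comparison.

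Sections 4.2 and 4.3 say that placebo is included so that activity can be interpreted against a control. Section 9.1 states: "This is not a hypothesis testing study". Section 9.5 leaves the SAP to be finalised before database lock and describes the sections that follow as a summary of the planned analyses.

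**The concern.** Two things weaken the efficacy reading.

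The first is precision. Entry requires "a CLASI-A score of 4 or higher at the time of Screening and randomization", with no upper limit, so all three severity bands in Section 8.6.1 (0 to 9, 10 to 20 and 21 to 70) are eligible. Absolute improvement is bounded by the starting score: a subject who enters at 4 can improve by at most 4 points. Sections 6.3.1 and 8.5 name no stratification factor. With 8 placebo subjects, a chance imbalance in baseline carries into a difference in change scores, although the baseline value is already collected and could be used to remove much of it.

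The second is bias. Change within the active arm includes placebo response, natural fluctuation and the effect of background therapy. Counting it as evidence, without placing it below the placebo comparison, undercuts the reason the protocol gives for having a placebo arm. The formal status of the study is exploratory, but a development decision rests on the size of the effect.

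**Working it through.** **Inputs from the protocol.** Section 9.2: "The study will enroll up to 24 subjects with SLE in 2 parallel arms randomized to receive 2:1 DS-7011a or placebo". At full enrolment that is 24 × 2/3 = 16 and 24 × 1/3 = 8; the arm sizes are derived, not printed. No alpha, power, effect size, SD or correlation is stated, and the sample size is expressly not based on power. There is therefore no calculation of the plan's own to reproduce.

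**Assumptions.** Equal variance σ² at baseline and follow-up, a linear relation with correlation ρ, and approximate normality. The values of ρ are assumed.

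**Step 1: chance imbalance at baseline.** The SE of the difference in baseline means is SD × √(1/16 + 1/8) = 0.433 SD. The chance of an imbalance of at least 0.5 SD in either direction is 2 × [1 − Φ(0.5/0.433)], or about 25%.

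**Step 2: precision of the between-arm difference.** In units of σ² × (1/16 + 1/8):
- change score: 2(1 − ρ)
- ANCOVA: (1 − ρ²) × (N − 3)/(N − 4), where the last factor is 21/20 = 1.05 and allows for estimating the slope in 24 subjects
- ratio: 1.05 × (1 + ρ)/2

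| Assumed ρ | Change score | ANCOVA | Ratio | Variance cut | Change-score N with equal precision (24/ratio) | 95% CI narrower by |
|---|---|---|---|---|---|---|
| 0.3 | 1.40 | 0.956 | 0.68 | 32% | 35 | 17% |
| 0.5 | 1.00 | 0.788 | 0.79 | 21% | 30.5 | 11% |
| 0.7 | 0.60 | 0.536 | 0.89 | 11% | 27 | 5% |
| 0.9 | 0.20 | 0.200 | 1.00 | none | 24 | none |

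Example at ρ = 0.5: the 95% half-width is 2.074 × 0.433 × √1.00 = 0.90 SD for the change score (22 df) and 2.080 × 0.433 × √0.788 = 0.80 SD for ANCOVA (21 df). A simulation of 20,000 trials at 16 versus 8 gave variance ratios of 0.68, 0.79 and 0.90 for ρ = 0.3, 0.5 and 0.7.

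**Step 3: pre/post change when the drug does nothing.** Suppose subjects improve by k SDs of change for non-drug reasons. A paired t statistic in n = 16 has 15 df and noncentrality k√16 = 4k. The probability that it exceeds 2.131 is:

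| Assumed k | Within-arm comparison favourable at p<0.05 |
|---|---|
| 0.25 | 15% |
| 0.5 | 46.5% |
| 0.75 | 80% |
| 1.0 | 96% |

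The improvement is common to both arms under randomisation, so the active-minus-placebo contrast stays at its nominal two-sided 5% throughout. The test is used here only as a gauge of how often the result would look convincing.

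**Step 4: how much could come from the entry threshold alone.** Selecting on CLASI-A of at least 4 at two visits, with assumed means of 6 to 10, SDs of 4 to 6 and retest correlations of 0.5 to 0.9, gives regression to the mean of about 0.1 to 0.8 points, or 0.04 to 0.21 SD of change. That lies below the first row of the Step 3 table. The larger rows would need placebo response, natural fluctuation or background care.

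**The case against.** The strongest reply is that a randomised comparison is planned, the study tests no hypothesis, and Section 9.5 leaves detail to a later SAP. Much of this stands, and it limits the point in four ways.

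- A reader might infer that pre/post change replaces the placebo comparison. It does not: Sections 9.2, 9.5.1 and 9.5.5 all plan a comparison between arms. The gap is that the two are not ranked.
- A reader might infer that the plan commits to raw change scores. That rests on silence. The estimator is unspecified, so adjustment is not prespecified rather than ruled out. With no formal test, the cost is a wider interval.
- A reader might infer that the entry threshold produces a large spurious improvement. Step 4 shows that part is small.
- Section 3.1 says "Anti-Sm and anti-RNP autoantibodies will be assessed with particular interest", and a reader might infer that seronegative subjects dilute the autoantibody result by a known amount. The documents do not support a figure. The target of 9 subjects is tentative and covers either antibody, Section 9.5.1 does not say how these values will be averaged, and any dilution factor needs an assumed change in negative subjects.

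A further objection is technical. If response is proportional to baseline, additive ANCOVA on raw scores is not the most efficient choice. In one simulated setting (assumed skewed baselines of 4 to 50, response SD 0.35, drug effect of 30 percentage points), power was about 31% for raw change, 38% for ANCOVA and 48% for percentage change. The ANCOVA-to-change variance ratio was 0.81 with that effect and 0.89 without, and the gain shrinks if the assumed placebo improvement is smaller. So ANCOVA is not the only defensible choice, but even here it does better than the unadjusted difference.

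The reply does not remove the main difficulty. Section 9.2 attaches a development decision to the extent of the effect, and nothing in the available text fixes which estimate of it will be read.

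**Conclusion.** The point holds as a gap in prespecification. Section 9.5.1 names no baseline adjustment, and Section 9.2 admits uncontrolled change as evidence without subordinating it to the randomised contrast that Sections 4.2 and 4.3 rely on.

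The precision gain from adjustment is a variance cut of roughly 11% to 32% for correlations of 0.7 down to 0.3, and nothing near 0.9. These figures assume full enrolment at 16 versus 8, no dropout, and the equal-variance linear model. The pre/post risk depends wholly on the size of the non-drug improvement, which the documents do not give: 15% to 96% over the range examined, and 46.5% at 0.5 SD of change.

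The change is advisable before database lock. The omission does not invalidate the study.

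**What to change.** - **Section 9.5.1:** estimate the active-minus-placebo CLASI-A difference by ANCOVA with baseline CLASI-A as covariate, and report a 95% CI with small-sample degrees of freedom. Make Day 85 the decision visit, since it is the three-month point that Section 4.2 justifies. State the scale of analysis (absolute or percentage change) at the same time. Do the same for other continuous endpoints that have a baseline value.
- **Section 9.2:** make this adjusted between-arm difference the efficacy reading for go/no-go, and label within-arm pre/post change as descriptive only.
- **CGI-C and PGI-C:** leave these out of the adjustment and compare them as observed. Sections 8.6.6 and 8.6.7 define them as ratings of change, so a Day 1 entry in Table 1.1 is not a baseline severity.
- **Pharmacodynamic endpoints:** do not impose one repeated-measures model over Days 29 to 113. Section 8.7.2 collects skin mRNA only on Days 1, 85 and 113, and gene signatures also on Days 2 and 8.

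The cost is one degree of freedom, some SAP wording and minor programming. No new data or visits are needed.

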		Day 1	Day 2	Day 8	Day 29	Day 57	Day 85	Day 113	Day 169
				±1 day	±2 days	±3 days	±3 days	±3 days	±3 days
Lymphocyte Subsets (CD3-, CD4-, CD8-, CD20-, CD16-, CD56-positive) (central laboratory)	X	X ^c			X ^c	X ^c	X	X	
Randomization and Study Drug Administration									
Randomization		X							
Study Drug Administration		X			X	X			
Pharmacokinetics									
Plasma DS-7011a (central laboratory) ^d		X	X	X	X	X	X	X	
Pharmacodynamic and Other Biomarkers									
ESR and CRP (local laboratory)	X	X ^c			X ^c	X ^c	X	X	
Complement Factors (C3 and C4) (local laboratory at Screening and central laboratory thereafter)	X	X ^c			X ^c	X ^c	X	X	
SLE-related Autoantibodies (anti-nuclear, anti-dsDNA, anti-Sm, anti-RNP) (local laboratory at Screening and central laboratory thereafter)	X	X ^c			X ^c	X ^c	X	X	
TLR7 and IFN-Type I GS		X ^c	X	X	X ^c	X ^c	X	X	
Cytokines (central laboratory)		X ^c			X ^c	X ^c	X	X	
Skin Tape Harvesting for mRNA (central laboratory)		X					X	X	
Immunogenicity									
Anti-drug Antibodies (central laboratory)		X ^c			X ^c	X ^c	X	X	X ^e
Pharmacogenetics									
Blood sample for genotyping (central laboratory)		X ^c							

	Screening Period	Treatment Period						Follow-up Period ^a	
								EOT Visit	EOS Visit
Study Assessments and Tests	Within 4 weeks (28 days) prior to randomization	Week 0	Week 0	Week 1	Week 4	Week 8	Week 12	Week 16	Week 24
		Day 1	Day 2	Day 8	Day 29	Day 57	Day 85	Day 113	Day 169
				±1 day	±2 days	±3 days	±3 days	±3 days	±3 days
Patient Reported Outcome Questionnaires									
Quality of life questionnaires (Skindex-29+3 and SF-36)		X			X	X	X	X	
FACIT-Fatigue		X			X	X	X	X	
Itch NRS		X			X	X	X	X	
Patient's Global Impression of Change		X			X	X	X	X	

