8.6.6. Clinician's Global Impression of Change

Clinician's Global Impression of Change (CGI-C) is a brief rating scale to reflect the clinician's evaluation on the changes in SLE disease severity. The investigators are asked to rate disease progress at each visit based on their clinical judgment as "very much worse", "much worse", "minimally worse", "no change", "minimally improved", "much improved", "very much improved".¹¹

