The Functional Assessment of Chronic Illness Therapy-Fatigue (FACIT-F) is a 13-item questionnaire that assesses self-reported fatigue and its impact upon daily activities and function.²⁴ It uses a 5-point Likert-type scale (0 = not at all; 1 = a little bit; 2 = somewhat; 3 = quite a bit; 4 = very much). As each of the 13 items of the FACIT-Fatigue scale ranges from 0 to 4, the range of possible scores is 0 to 52, with 0 being the worst possible score and 52 the best. To obtain the 0 to 52 score, each negatively worded item response is recoded so that 0 is a bad response and 4 is good response. All responses are added with equal weight to obtain the total score. Fatigue is among the most prevalent symptoms of SLE, and can have profound effects on subjects' Health-Related Quality of Life (HRQoL).^{24,25} The FACIT-Fatigue has been validated in subjects with SLE and is considered a valid and responsive measure of fatigue in subjects with SLE.^{26,27,28,29}

- Itch Numeric Rating Scale

The Itch Numeric Rating Scale (NRS) is a self-rated single item scale designed for assessing worst itch in the past 7 days. The scale utilizes an 11-point NRS, scored from 0 (no itch) to 10 (worst imaginable itch).

- Patient's Global Impression of Change

The Patient's Global Impression of Change (PGI-C) is a self-rated scale that ask respondents to describe the retrospective change in their lupus skin symptoms at a given time point. Responses are captured on a 7-point scale, as follows: "very much worse", "much worse", "minimally worse", "no change", "minimally improved", "much improved", "very much improved".³⁰

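### CGI-C and PGI-C already rate change, yet section 9.5.1 compares the arms on their change from a Day 1 rating

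*Combined protocol and SAP*

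**What the plan says.** Section 8.6.6 says that CGI-C "is a brief rating scale to reflect the clinician's evaluation on the changes in SLE disease severity". On how it is rated, it says: "The investigators are asked to rate disease progress at each visit based on their clinical judgment". Section 8.6.7 says that PGI-C asks respondents to "describe the retrospective change in their lupus skin symptoms at a given time point". Both use the same seven categories, with 'no change' in the middle. Neither section says which earlier time the rater should compare with.

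In Table 1.1 (section 1.3), the rows for CGI-C and "Patient's Global Impression of Change" are blank at Screening and marked on Days 1, 29, 57, 85 and 113. The note to Figure 1.1 labels Day 1 as Baseline, and it is the first dosing day.

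Section 9.5.1 plans two things for the efficacy endpoints. It first summarises them by treatment group with descriptive statistics. It then summarises the comparison between groups for "change from baseline to each visit in CLASI-A, CLA-IGA, SLEDAI-2K, PGA-SLE, CGI-C, and PROs". PGI-C is not named there, but Table 3.1 and section 8.6.7 list it among the PROs. No exception is made for either change scale.

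**The concern.** Change from baseline makes sense for a scale that records status, such as CLASI-A or SLEDAI-2K. CGI-C and PGI-C record change directly, so subtracting a Day 1 rating gives the difference between two changes, each over its own recall period. On Day 1 there is no treatment period to rate, so that rating can only describe change since some earlier time that the protocol does not define.

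At stake is the meaning of two clinical efficacy endpoints. Section 9.2 looks for initial efficacy in a consistent effect across several endpoints, both between arms and between baseline and later visits. An endpoint that is hard to read adds little to that argument and may blur it.

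**Working it through.** The plan gives no figure for these scales to reproduce: no SD, no correlation and no numeric coding. The check compares the sections and adds simple subtraction. The coding is an assumption: 'very much worse' = −3, 'no change' = 0, 'very much improved' = +3, equally spaced.

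Let D = (rating at a later visit) − (rating on Day 1).

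1. **Every Day 1 rating is 'no change'.** D = later rating − 0 = later rating. The Day 1 item and the subtraction add nothing. No section requires this rating on Day 1.

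2. **Day 1 ratings differ.** D can run from −3 − 3 = −6 to 3 − (−3) = +6, and one value of D covers different states. A subject going from 'minimally improved' to 'much improved' has D = 2 − 1 = +1. A subject going from 'minimally worse' to 'no change' has D = 0 − (−1) = +1.

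3. **The meaning depends on the unstated reference point.** Take a subject rated 'much improved' (+2) on Day 1.
   - If later ratings keep the same pre-study reference and the gain is simply held, the later rating is +2 and D = 2 − 2 = 0. That is a fair result, since nothing improved after dosing.
   - If later ratings refer to Day 1 and the gain is held, the later rating is 0 and D = 0 − 2 = −2. A stable course looks like a worsening.
   - If later ratings refer to Day 1 and the subject improves further to +2, D = 2 − 2 = 0. A real gain after dosing disappears.

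4. **Effect on the comparison between arms.** The expected difference in D is (expected later rating, active − placebo) − (expected Day 1 rating, active − placebo). If Day 1 is rated before the infusion, randomisation makes the second bracket zero in expectation. The comparison is then unbiased for the difference in later ratings.

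5. **Chance imbalance.** With 24 subjects at 2:1 there are 16 active and 8 placebo. If one placebo subject has +2 on Day 1 and all others have 0, the placebo mean of D moves by −2/8 = −0.25 category. The same rating in the active arm moves that mean by −2/16 = −0.125. This is pre-treatment noise and is as likely to fall in either direction.

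**The case against.** The strongest reply is that little is lost. Section 9.5.1 already summarises the observed ratings by arm, so a readable result exists alongside the derived one. There is no primary efficacy analysis, section 9.1 says that no hypothesis is tested, and section 9.2 puts CLASI-A and the mechanistic endpoints in front. Section 9.5 also leaves detail to an SAP to be finalised before database lock, which could drop the subtraction. All of this stands and lowers the severity. It does not remove the inconsistency, because nothing in the supplied text exempts the two scales.

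It can also be said that Day 1 ratings will cluster at 'no change', since allowed SLE medication must have been stable for at least 4 weeks. That is plausible but not assured: exclusion criterion 12 also requires topical corticosteroids to be stopped 2 weeks before randomisation, which could affect skin symptoms on Day 1.

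A reader might infer three stronger things that the documents do not support:

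- **That the results would be wrong or biased.** Step 4 of the working shows no bias in the expected difference between arms.
- **That precision falls by a known amount, for instance that 24 subjects behave like 12.** This needs equal SDs on Day 1 and later, and zero correlation between them. The documents give neither. With equal SDs and a correlation of 0.5 there is no loss at all, because 2 × (1 − 0.5) = 1.
- **That raters will have no reference point, so that a sustained response is recorded as 'no change' at Day 113.** The protocol text is silent, but it describes the instruments without reproducing the forms, and these may state one.

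**Conclusion.** The point holds as an inconsistency between the scales' definitions and their planned analysis. Change from baseline in CGI-C and PGI-C is redundant if all Day 1 ratings are 'no change'. Otherwise it mixes two recall periods, is hard to read for a single subject or within an arm, and can add noise. The size of that noise cannot be stated from the documents.

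Severity is moderate to minor, because both endpoints are secondary and descriptive and their observed ratings are also summarised. The absence of bias rests on the Day 1 rating being made before the first infusion; Table 1.1 does not give its timing within the day. The numerical examples rest on the assumed −3 to +3 coding.

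**What to change.** 1. In section 9.5.1, remove CGI-C from the change-from-baseline comparison and exempt PGI-C from the PROs there. Compare the arms on the observed ratings, as n and % per category, at Days 29, 57, 85 and 113. Carry the same rule into the SAP.
2. In Table 1.1, delete the Day 1 mark for both scales, or state what the Day 1 rating is for.
3. In sections 8.6.6 and 8.6.7, name Day 1, before the first infusion, as the reference point for both scales, and check that the administered forms agree. With that reference, each observed rating is itself the change since baseline, so no subtraction is needed for the within-arm comparison in section 9.2.

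The cost is small: a few lines of wording, one schedule edit and slightly less data collection. Day 1 ratings already collected would stay in the database unused. The reference point should be settled early, because ratings already made against a different one cannot be corrected in the analysis.
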